### **5.4 Pharmacokinetics**

Not applicable. Pharmacokinetic samples will not be taken during the study.

### **5.5 Pharmacodynamics**

Not applicable. Pharmacodynamic samples will not be taken during the study.

### **5.6 Pharmacogenetics**

Not applicable. Pharmacogenetic samples will not be taken during the study.

### **5.7 Biomarker Analysis**

Not applicable. There will be no collection and storage of donated biological samples for exploratory biomarker analysis.

## **6. SAFETY REPORTING AND MEDICAL MANAGEMENT**

The Principal Investigator is responsible for ensuring that all staff involved in the study are familiar with the content of this section.

Please refer to section 4.2.2 and 5.1.2 for detail of how serious arrhythmias are detected and treated per the safety protocol and refer to section 5.3.2 for Patients with Intra-Dialytic Arrhythmias. ILR will be interrogated weekly following the long “dialysis weekend” using the Patient Connector and the CareLink Express mobile app on a tablet. Cardiac data will be

managed via the CareLink network and reviewed by the Medtronic Monitoring Service, where clinically relevant cardiac data will be identified and prioritized based on clinically actionable events. If a patient's arrhythmia meets any of the three CSCA categories, the principal study cardiologist and the site PI will be contacted to determine whether the patient requires further evaluation. Participating sites will receive copies of relevant cardiac events to enter into their patient's medical records.

## **6.1 Definition of Adverse Events**

An adverse event is the development of an undesirable medical condition or the deterioration of a pre-existing medical condition following or during exposure to a pharmaceutical product, whether or not considered causally related to the product. An undesirable medical condition can be symptoms (e.g., nausea, chest pain), signs (e.g., tachycardia, enlarged liver) or the abnormal results of an investigation (e.g., laboratory findings, electrocardiogram). In clinical studies, an AE can include an undesirable medical condition occurring at any time, including run-in or washout periods, even if no study treatment has been administered.

The term AE is used to include both serious and non-serious AEs.

## **6.2 Definitions of Serious Adverse Event**

A serious adverse event (SAE) is an AE occurring during any study phase (i.e., run-in, treatment, washout, follow-up), that fulfils one or more of the following criteria:

- Results in death
- Is immediately life-threatening
- Requires in-patient hospitalization or prolongation of existing hospitalization
- Results in persistent or significant disability/incapacity or substantial disruption of the ability to conduct normal life functions
- Is a congenital abnormality or birth defect
- Is an important medical event that may jeopardize the patient or may require medical intervention to prevent one of the outcomes listed above.

Note: Adverse events of malignant tumors reported during a study should generally be assessed as SAEs. If no other seriousness criteria apply, the 'Important Medical Event' criterion should be used. In certain situations, however, medical judgement should be applied to clarify that the malignant tumour is a non-serious AE. For example, progression of a pre-existing tumour (i.e., included as medical history) during the study, that does not change treatment and/or prognosis of the malignant tumour, would be reported as an AE, but may not qualify for being assessed as serious. Also, some types of malignant tumors, which do not spread remotely after a routine treatment that does not require hospitalization, may be assessed as non-serious; examples include Stage 1 basal cell carcinoma and Stage 1A1 cervical cancer removed *via* cone biopsy.

The causality of SAEs (their relationship to all study treatment/procedures) will be assessed by the Investigator and reported to the Sponsor.

For further guidance on the definition of a SAE, see [Appendix A](#) (Additional Safety Information).

### **6.3 Definition of Suspected Unexpected Serious Adverse Event (SUSAR)**

A suspected adverse reaction related to an Investigational Product (IP) that is both unexpected and serious.

### **6.4 Recording of adverse events**

#### **6.4.1 Time period for collection of adverse events**

Adverse events will be collected from the time of first dose of Lokelma®, throughout the treatment and post-treatment follow-up period, up to the last study visit.

SAEs will be reported from the time the patient signed the Informed Consent Form.

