
To evaluate whether the use of Lokelma during periods when patients are receiving a 3.0 K+/2.5 Ca++ bath is associated with hypokalemic events defined as K+ <3.5 mEq/L.
	
 
➤ Total number of hypokalemic events defined as Piccolo Point of Care Testing (POCT) or laboratory-measured K+ of < 3.5 mEq/L.
 

Safety Objective #2: Incidence of Dialysis-related Hypokalemia, Hypomagnesemia, Hypophosphatemia, or Low Calcium	Safety Outcome Measure:

To determine the levels of K+, Mg++, calcium and PO4 during dialysis (measured promptly prior to the termination of dialysis) during experimental treatment [2] compared to standard treatment [3].
 
Note: Each electrolyte is its own "safety" objective independently.
	
➤ Number of events (measured promptly prior to the termination of dialysis) where a Piccolo POCT measurement of K+ is < 3.5 mEq/L OR Ca++ is < 7.0 mEq/L, OR Mg++ is < 2.0 mg/dl OR a PO4 level is <3.0 mEq/L.
 
All episodes where a specific electrolyte falls below the above listed threshold will be considered an "event" for that electrolyte. The total number of "events" will be recorded during the 8-week Treatment Phase-1 and the 8-week Treatment Phase-2 cross-over periods.

Safety Objective #3: Adverse Experiences
	
Safety Outcome Measure:

To evaluate the safety and tolerability of the experimental treatment [2] compared to standard treatment [3] based on the frequency of reported adverse experiences.
	
➤ Frequencies of AEs, SAEs, and withdrawals due to AEs, with focus on treatment-related events.

Exploratory Objectives:
	
Exploratory Outcome Measures:

1) To evaluate the relationship between protein-bound uremic toxins (PBUTs) and atrial fibrillation rates. PBUTs such as indoxyl sulfate (IS) and p-Cresol sulfate (PCS) can induce atrial fibrillation (Aoki et al. 2015; Tang et al. 2015).
	
➤ Correlation between PBUTs (IS, PCS, and ADMA) and the frequency of atrial fibrillation events.

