## 2.3 Safety Objectives

Safety Objective #1: Lokelma-Induced Hypokalemia	Safety Outcome Measure:
To evaluate whether the use of oral sodium zirconium cyclosilicate (Lokelma ® ) during periods when patients are receiving a 3.0 K + /2.5 Ca ++ dialysate bath is associated with hypokalemic events defined as K + <3.5 mEq/L.	➤ Total number of hypokalemic events defined as Piccolo POCT or laboratory-measured K + of < 3.5 mEq/L.
Safety Objective #2: Incidence of Dialysis-related Hypokalemia, Hypomagnesemia, Hypophosphatemia, or Low Calcium	Safety Outcome Measure:
To determine the levels of K + , Mg ++ , calcium and PO 4 during dialysis (measured promptly prior to the termination of dialysis) during experimental treatment [2] compared to standard treatment [3]. Note: Each electrolyte is its own "safety" objective independently.	➤ Number of events (measured promptly prior to the termination of dialysis) where a Piccolo POCT measurement of K + is < 3.5 mEq/L OR Ca ++ is < 7.0 mEq/L, OR Mg ++ is < 2.0 mg/dl, OR a PO 4 level is <3.0 mEq/L. All episodes where a specific electrolyte falls below the above listed threshold will be considered an "event" for that electrolyte. The total number of "events" will be recorded during the 8-week Treatment Phase-1 and the 8-week Treatment Phase-2 cross-over periods.
Safety Objective #3: Adverse Experiences	Safety Outcome Measure:
To evaluate the safety and tolerability of the experimental treatment [2] compared to standard treatment [3] based on the frequency of reported adverse experiences.	➤ Frequencies of AEs, SAEs, and withdrawals due to AEs, with focus on treatment-related events.

Abbreviations: AE=adverse event; CSCA=clinically significant cardiac arrhythmia; SAE=serious adverse event

[2] Experimental treatment (8 weeks): hemodialysis using 3.0K+/2.5 Ca++ dialysate bath, with sodium zirconium cyclosilicate (Lokelma®) supplementation on off-treatment days

[3] Standard treatment (8 weeks): hemodialysis using 2.0K+/2.5 Ca++ dialysate bath, without sodium zirconium cyclosilicate (Lokelma®) supplementation

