**Table 1 Study Plan and Schedule of Assessments**

Study Period / Visit	Screening	ILR Insertion by EP cardiologist	Baseline/ Randomization	New Dialysate Accommodation Period 1	Treatment Phase 1	Cross-over	New Dialysate Accommodation Period 2	Treatment Phase 2	ILR Removal by EP cardiologist	End of Study	Reference to Protocol Section
Study Week (Wk) [* , ** or ***]	-4 to -3**	-2*	1**	1 & 2**	3 to 10**	11**	11 & 12**	13 to 20**	21-22*	22-23***	
Study Day (D)	-28 to -15	-14	1	1 to 14	15 to 70	71	71 to 84	85 to 140	Between D141 and D155	Within 1 to 14 days after ILR Removal	
Blood samples for PBUTs [3]					X						4.2.1
Day of the Week			M/T	M/T	M/T	M/T	M/T	M/T			
Local laboratory Mg ++ promptly before dialysis end) [4]				X	X		X	X			4.2.1
Adverse event recording & review [8]				X	X	X	X	X	X	X	6.4
Serious Adverse event recording & review [9]	X	X	X	X	X	X	X	X	X	X	6.4
Concomitant medication	X	X	X	X	X	X	X	X	X	X	5.2.5, 7.7
Local laboratory Mg ++ promptly before dialysis end) for muscle cramping [5]				X	X		X	X			4.2.1

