[2] During the treatment period (both 2-week accommodation periods and 8-week Treatment phases), a second Piccolo POCT is performed promptly before dialysis end and within 30 minutes prior to rinse back on Mondays or Tuesdays after each long dialysis weekend (i.e., weekly), to measure K+, Ca++ and PO4.

[3] Applies only to the first twenty-five (25) patients randomized receiving standard treatment (hemodialysis using 2.0K+/2.5 Ca++ dialysate bath, without Lokelma supplementation) during Treatment Phase-1. Performed weekly, on Mondays or Tuesdays after each long dialysis weekend, promptly before dialysis end and within 30 minutes prior to rinse back.

[4] Performed weekly, on Mondays or Tuesdays after each long dialysis weekend, promptly before dialysis end and within 30 minutes prior to rinse back. Mg++ levels will be determined by the local laboratory at each site.

[5] Performed (if possible) upon symptomatic muscle cramping, promptly before dialysis end and within 30 minutes prior to rinse back. Mg++ levels will be determined by the local laboratory at each site.

[6] Baseline/Randomization is conducted on Week 1 of the new Dialysate Accommodation Period 1. Crossover occurs on the same day as Week 11 of the new Dialysate Accommodate Period 2. Neither Baseline/Randomization nor Crossover will be considered a separate visit.

[7] If ILR insertion is performed more than 30 days after the last K+ Piccolo POCT determination, please contact the sponsor who will determine if an additional K+ Piccolo POCT determination will be required prior to the baseline visit. These will be handled on a case-by-case basis.

[8] Adverse events will be collected from the time of first dose of Lokelmaâ, throughout the treatment and post-treatment follow-up period, up to the last study visit.

[9] SAEs will be reported from the time the patient signed the Informed Consent Form.

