**Figure 10 – Patient Assistant**

### **4.2.3 Cross-Over (Week 11)**

At the end of the first treatment phase (Weeks 3 to 10) of the study, all blood draws will be stopped for 2 weeks. Cardiac loop recording devices will not be interrogated during this 2-week accommodation period, and the data recorded during that time will not be used for analysis. Patients who completed treatment with experimental 3.0 K+/2.5 Ca++ dialysate with Lokelma supplementation (on off-dialysis days) during Treatment Phase-1 will be crossed over to standard 2.0 K+/2.5 Ca++ dialysate with no Lokelma supplementation for Treatment Phase-2. Patients who completed treatment with standard 2.0 K+/2.5 Ca++ dialysate with no Lokelma supplementation during Treatment Phase-1 will cross-over to experimental 3.0 K+/2.5 Ca++ dialysate with Lokelma supplementation (on off-dialysis days) for Treatment Phase-2.

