#### **8.3.3 Safety Analysis Set**

The Safety Analysis Set will include all randomized participants who during the first treatment period (study Phase I): (i) received at least one dose of the study drug (Lokelma) during treatment with the 3.0 K+ dialysate bath; or (ii) completed Visit 2 during treatment with the 2.0 K+ dialysate bath. All safety endpoints will be analyzed using the SAS.

The number of participants in each analysis set, and the number excluded and associated reasons will be summarized by treatment group and overall. In addition, the following periods will be defined for the purpose of reporting:

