#### **8.5.6 Safety Analyses**

Lokelma-induced hypokalemia will be evaluated based on the total number of hypokalemic events defined as PiccoloPOCT or laboratory-measured K+ of < 3.5 mEq/L.

The incidence of dialysis-related hypokalemia, hypomagnesemia, hypophosphatemia, and low calcium will be evaluated based on the number of events promptly prior to the termination of dialysis where a PiccoloPOCT measurement of K+ is < 2.0 mEq/L OR Ca++ is < 7.0 mEq/L, OR Mg++ is < 2.0 mg/dl, OR a PO4 level is < 3.0 mEq/L. All episodes where a specific electrolyte falls below the above listed threshold will be considered an “event” for that electrolyte. The total number of “events” will be recorded during the 8-week Treatment Phase-1 and the 8-week Treatment Phase-2 cross-over periods and compared between the treatments.

Safety will also be assessed in terms of the frequency of AEs, SAEs, and withdrawals due to AEs, with focus on treatment-related events. Appropriate summaries of these data will be presented by treatment group and/or study period.

Adverse events will be coded using the Medical Dictionary for Regulatory Activities (MedDRA) system organ class (SOC) and preferred term (PT). A treatment-emergent AE

(TEAE) is defined as an AE with the start date on or after the first dose date and up to (and including) 14 days after the last dose date in each of study periods when patients received 3K Bath with Lokelma. However, when patients received 2K Bath without Lokelma, A treatment-emergent AE (TEAE) is defined as an AE with the start date on or after the first visit date and up to (and including) 14 days after the last visit date in each of study periods. Only TEAEs will be included in table summaries.

The number and percentage of participants experiencing AEs, SAEs, AEs that led to withdrawal, AEs that led to death, and the number of such events, will be summarised by SOC, PT, and treatment group and study period. The number and percentage of participants experiencing AEs will further be summarised by intensity and will be presented with the number of events at each level of intensity.

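### Non-serious AE collection starts at the first Lokelma dose, so as written it omits the whole first period for patients who begin on the control bath

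*Protocol*

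**What the plan says.** Section 6.4.1 sets the start of AE collection: "Adverse events will be collected from the time of first dose of Lokelma". From that point collection runs through treatment and follow-up to the last study visit. The next sentence gives SAEs a different start, the signing of consent. Footnote [8] to Table 1 repeats the AE rule and is attached to the adverse event row. That row is marked from Accommodation Period 1 onward and is not split by sequence.

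In the control-first sequence there is no Lokelma before cross-over. Section 4.2.3 says that patients on "dialysate with no Lokelma supplementation during Treatment Phase-1 will cross-over to experimental" treatment afterwards, and Table 1 puts the cross-over at Day 71. (I write control-first because Table 4 in section 8.3.3 reverses the letters A and B used in sections 1.4 and 3.5.)

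Other sections expect AE data from that period:

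- Safety Objective #3 (Synopsis) is "To evaluate the safety and tolerability of the experimental treatment [2] compared to standard treatment [3] based on the frequency of reported adverse experiences".
- Section 8.5.6, for the "2K Bath without Lokelma, A treatment-emergent AE (TEAE) is defined as an AE with the start date on or after the first visit date", and it summarises AEs by treatment group and study period.
- Section 8.3.3 admits control-first patients to the Safety Analysis Set once they have "completed Visit 2 during treatment with the 2.0 K + dialysate bath" in the first period.

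**The concern.** A collection window that opens with a drug taken on only one of the two regimens opens at different times in the two sequences. For Lokelma-first patients it opens almost at randomization. For control-first patients it opens about ten weeks later. Under the literal rule, all non-serious AE data on the control regimen would come from Phase 2 patients who had already taken Lokelma. Phase 1 is the only period in which control patients have had no study Lokelma, and it would contribute no non-serious events on the control side.

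The loss runs one way: it lowers the control count and makes the experimental regimen look worse. A control-first patient who leaves before cross-over stays in the Safety Analysis Set with no non-serious AE window at all, apart from the question about AEs asked when consent is withdrawn (3.10.2). The trial has no data monitoring committee, and section 6.10 relies on quarterly reviews of safety data that may lead to protocol changes, so one-sided collection could also mislead those reviews.

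**Working it through.** **Inputs.** 44 patients per sequence (8.2). Study days from Table 1. Dosing on off-dialysis days (7.2.1), with visits on the Monday or Tuesday after the long interval. Equal true AE rates on both regimens are assumed throughout.

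**Timeline.** (2 + 8) weeks × 7 = Day 70 for the end of the first period, so cross-over is Day 71, as in Table 1. The second period runs over Days 71 to 140.

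**Planned exposure.** 2 × 44 × 70 = 6,160 patient-days per regimen.

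**Days without non-serious AE collection under the literal rule**, with the first dose on the first off-dialysis day (Day 2 or Day 72):

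- Control: 44 × 70 = 3,080, and 3,080 / 6,160 = 50%.
- Experimental: 44 × 1 + 44 × 1 = 88, and 88 / 6,160 = 1.4%.

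**Apparent count ratio, experimental / control:** (6,160 − 88) / (6,160 − 3,080) = 6,072 / 3,080 = 1.97.

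**Range.**

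| Variation | Calculation | Ratio |
|---|---|---|
| Rule followed for 25%, 50%, 75% of patients in each sequence (assumed share p) | (6,160 − 88p) / (6,160 − 3,080p) | 1.14, 1.32, 1.58 |
| All AEs, with 10%, 20%, 30% serious and so collected (assumed share s) | [s + (1 − s) × 0.9857] / [s + (1 − s) × 0.5] | 1.79, 1.65, 1.52 |
| 8-week phases only | 4,928 / (4,928 − 2,464) | 2.00 |
| Lokelma begins only with the 8-week phase (Day 16 or 86) | (6,160 − 88 × 15) / 3,080 = 4,840 / 3,080 | 1.57 |
| 10% attrition (8.2), placed at cross-over (assumed) | (44 × 69 + 39.6 × 69) / (39.6 × 70) = 5,768 / 2,772 | 2.08 |

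The fourth row is there because section 7.2.1 ties dosing to the 8-week phase, while the Duration of treatment section and the dispensing row of Table 1 place it from accommodation. Those passages need reconciling; the gap exists under either reading. In the last row, 3,080 of 44 × 70 + 39.6 × 70 = 5,852 control days are lost (52.6%), and 44 × 0.1 = 4.4 control-first patients never reach a collection window.

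**With the 8.5.6 windows instead of the planned periods.** Take last 2.0 K+ visits on Days 64 and 134, last doses on Days 70 and 140, and the 14-day tail. For one patient from each sequence, the control window is 78 + 78 = 156 days. Of these, 7 (Days 72 to 78, control-first) + 78 = 85 are collected, a loss of 71 / 156 = 45.5%. The experimental window is 83 + 83 = 166 days, all collected. The ratio is 166 / 85 = 1.95.

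**After the change.** Lost days are 0 of 6,160 on each regimen and the ratio is 1.00. With the 8.5.6 windows it is 166 / 156 = 1.06, because the tails differ in length between regimens, not because of collection.

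**The case against.** The strongest reply is that sites would collect these events anyway. Section 6.4.5 tells them, without conditions, to record every AE that is reported, elicited or observed, and section 6.1 says an AE can occur before any study treatment. This makes the all-sites case less likely, and 1.97 should be read as a ceiling. But neither section sets a start date, whereas 6.4.1 does. If sites resolve the conflict differently, collection varies by site in a way nobody can see.

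It is also fair that not every cited passage conflicts directly. The Safety Analysis Set defines a denominator, not a window, and the marks in the Table 1 row can be read together with their own footnote. The direct conflict is with the 2.0 K+ window in 8.5.6. Safety Objective #3 sets no window, but it cannot be met properly without these data.

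A randomized Phase 2 comparison of 44 against 44, before attrition, would survive, and section 8.5.1 assumes no carry-over. That is a real remainder. It is still half of the planned control experience, and a by-period table would reveal the missing half without supplying it.

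Finally, the stakes are bounded. SAEs, laboratory safety endpoints, loop-recorder arrhythmias, and intradialytic hypotension and cramping (5.1.4) are captured separately. Section 6.4.6 already keeps most non-serious laboratory and vital-sign changes out of AE reporting. The AE comparison is descriptive, and no primary or secondary result depends on it. This limits the severity but does not remove the fault.

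**Conclusion.** The concern holds. The collection rule in 6.4.1 and footnote [8] is wrong for a cross-over in which half the patients start without Lokelma, and it contradicts 8.5.6. The upper case is 50% of control patient-days without non-serious AE collection against 1.4% of experimental days, and an apparent count ratio of 1.97 where the true ratio is 1. That case rests on every site applying the rule literally, full follow-up, and dosing from accommodation. The partial-adherence shares, the serious-event shares and the timing of attrition are assumptions; the protocol does not give them. No figure is offered for the percentage of participants with an AE, which 8.5.6 also reports.

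The damage is confined to other non-serious AEs in a descriptive safety objective, so this should be fixed but does not threaten the trial's main results. It belongs in the protocol: a SAP can define windows and attribution but cannot restore events that were never recorded.

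**What to change.** Replace the start rule in section 6.4.1 and in Table 1 footnote [8] with one that does not depend on Lokelma, for example: *In both treatment sequences, AE collection begins at randomization (Study Day 1) and ends at the last study visit.* This covers both windows in 8.5.6 (first visit on the 2.0 K+ bath, first dose on the 3.0 K+ bath) and matches the marks in the Table 1 row. SAE reporting from consent is unchanged. Non-serious events between consent and Day 1 stay outside the window, as they do now; they precede randomization and do not enter the comparison. Assigning events near cross-over to a regimen can be left to the SAP.

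The cost is amendment wording, an eCRF instruction, and somewhat more AE entry for control-first patients in Weeks 1 to 10, at weekly visits that already take place. No visit, sample or procedure is added.
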